CMV = cytomegalovirus; COVID-19 = Coronavirus 2019; CTCAE = Common Terminology Criteria for Adverse Events; GI = gastrointestinal; PCR = polymerase chain reaction; PJP = *Pneumocystis jiroveci* infection; RNA = ribonucleic acid.

Table 10 Dose Modification/Toxicity Management Recommendations for Neutropenia

Adverse Reaction CTCAE V5.0 Grade/Severity	Recommended Management	Recommended Dosing Modification	Recommended Follow-up
Grade 1 or 2 Neutropenia (ANC of $\geq 1 \times 10^9/L$)	
 Monitor for any fever If persistent, consider supportive care as needed 	Continue current dose	
 In case of worsening of neutropenia or neutropenic fever, treat as Grade 3 or 4
Grade 3 Neutropenia (ANC of 0.5 to $1 \times 10^9/L$)	
 Monitor with complete blood count every 2 weeks Consider supportive care, including use of growth factors for patients with persistent or severe myelosuppression If persistent Grade 3, recurs or worsens, withhold study drug 	Continue current dose	
 On resolution to a lower grade or baseline, resume at the same dose level In case of recurrence after restarting treatment, consider next lower dose level at the discretion of the investigator In case of worsening of neutropenia or neutropenic fever, treat as Grade 4
Grade 4 Neutropenia (ANC of $< 0.5 \times 10^9/L$) OR Occurrence of neutropenic fever or infection	
 Monitor with complete blood count at least every 2 weeks Strongly recommend initiation of growth factors and other supportive care including antibiotic prophylaxis 	Withhold study drug	
 On resolution to a lower grade or baseline (ANC of $\geq 1 \times 10^9/L$), resume at the same dose level or at the next lower dose level at the discretion of the investigator (also refer to treatment guidelines for infection) In case of recurrence after restarting treatment, resume at the next lower dose level

ANC = absolute neutrophil count; CTCAE = Common Terminology Criteria for Adverse Events.

Table 11 Dose Modification/Toxicity Management Recommendations for Thrombocytopenia

Adverse Reaction CTCAE V5.0 Grade/Severity	Recommended Management	Recommended Dosing Modification	Recommended Follow-up
Grade ≤3 Thrombocytopenia without bleeding (Platelet count >25 × 10 ⁹ /L)	
 If persistent, consider supportive care as needed 	Continue current dose	
 In case of bleeding or worsening, manage as next higher grade
Grade 4 Thrombocytopenia (Platelet count <25 × 10 ⁹ /L) OR Any grade thrombocytopenia with bleeding	
 Monitor with complete blood count at least every 2 weeks Consider supportive care including platelet transfusion (as clinically indicated) On resolution to a lower grade or baseline, resume at the same dose level 	Withhold study drug	
 In case of recurrence after restarting treatment, consider next lower dose level at the discretion of the investigator

CTCAE = Common Terminology Criteria for Adverse Events.

Table 12 Dose Modification/Toxicity Management Recommendations for Rash and Cutaneous Skin Reactions

Adverse Reaction CTCAE V5.0 Grade/Severity	Recommended Management	Recommended Dosing Modification	Recommended Follow-up
Grade 1 or 2 Rash or Cutaneous Reactions (covering <30% of BSA, with no evidence of superinfection)	
 Initiate supportive treatment with emollients, antihistamines (for pruritus), or topical steroids Counsel patients to avoid skin irritants and sun exposure Monitor closely for any worsening 	Continue current dose	
 In case of worsening, treat as Grade 3 or 4
Grade 3 Rash or Cutaneous Reactions (covering >30% BSA, moderate/severe symptoms, associated with local superinfection)	
 Initiate supportive treatment with emollients, antihistamines (for pruritus), or topical steroids If rash doesn't resolve with topical steroids, consider low dose systemic steroids (0.5 to 1 mg/kg/day methylprednisolone IV or oral equivalent per institutional guidelines) Monitor closely for any worsening Consider skin biopsy and dermatology consult 	Withhold study drug	
 If resolved in less than 28 days, resume study drug at the same or a reduced dose as per investigator's discretion If not resolved within 28 days, permanently discontinue study drug. Treat as the next higher grade
Grade ≥4 (Life threatening) OR Any grade of SJS, TENS, or DRESS	
 Obtain skin biopsy and dermatology consult Treat as per the diagnosis and standard treatment guidelines (such as IV antibiotics and IV steroids) 	Permanently discontinue study drug	
 Continue close follow-up until resolution If improves to baseline, gradually taper steroids as per local standard

BSA = body surface area; CTCAE = Common Terminology Criteria for Adverse Events; DRESS = drug reaction with eosinophilia and systemic symptoms; IV = intravenous; SJS = Steven's Johnsons' Syndrome; TENS = toxic epidermal necrolysis.

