Grade 2 (Symptomatic, mild-to-moderate new or worsening symptoms)	
 • Educate patient to report any worsening immediately • Monitor for worsening symptoms (e.g., dyspnea/exertional dyspnea) every 3 days or as clinically indicated • Measure SpO2 as clinically indicated • Consider empiric antibiotics while evaluating the differential diagnosis • Request pulmonary and/or infectious disease consult if cause unclear • Evaluate differential diagnosis and causality (infection/immune-related/disease progression) with standard diagnostic tests, including but not limited to the following: 
 ○ Infectious panel (consider bacterial, viral, and opportunistic infections, including PJP and CMV-use of cultures) ○ Chest X-ray, SpO2, and HRCT ○ PFT and BAL, as necessary ○ ILD markers (KL-6 and SP-D), if available ○ COVID-19 testing (RT-PCR), if clinically indicated • If determined as infectious, prompt antibiotic, antifungal, or appropriate treatment as per standard guidelines 	
Withhold study drug
	
 • Continue close follow-up and re-imaging and increase steroid dose, as needed • If considered infectious etiology (clearly not immune related): 
 ○ If resolved in ≤7 days, resume study drug ○ If resolved in >7 to 28 days, resume study drug at the same or a reduced dose at the discretion of the investigator ○ If not resolved within 28 days or worsens, consider permanently discontinuing study drug • If considered non-infectious etiology with need for systemic steroid treatment, permanently discontinue study drug 
 ○ After sustained clinical improvement is observed, gradually taper steroids (e.g., by 5 to 10 mg/week over 4 to 6 weeks) per institutional standards ○ Patients can be switched to an equivalent/appropriate dose of oral

Adverse Reaction CTCAE V5.0 Grade/Severity	Recommended Management	Recommended Dosing Modification	Recommended Follow-up

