
Grade 3 or Grade 4
 
(Severe or life-threatening symptoms, new or worsening hypoxia)
	
 • Hospitalize for further management • Request pulmonary and/or infectious disease consult • Evaluate differential diagnosis and causality (as described above) • Prompt treatment with antibiotic, antifungal, or appropriate treatment as per standard guidelines • Prompt treatment with systemic steroids, if considered non-infectious or for suspected immune-related events 
 ○ Administer 1 to 2 mg/kg/day IV methylprednisolone or equivalent • Consider bronchoscopy and lung biopsy if clinically indicated 	
Withhold study drug
	
 • Continue close follow-up and re-imaging and increase steroid dose, as needed • If considered infectious etiology: 
 ○ If resolved to baseline within 28 days, resume study drug at a reduced dose ○ If not resolved within 28 days, permanently discontinue study drug. ○ If worsens or recurs on restarting treatment, permanently discontinue study drug • If considered immune-related or non-infectious etiology: 
 ○ Permanently discontinue study drug and treat promptly with steroids (including gradual tapering) 
 – If not improving after 48 hours or worsening, consider additional immunosuppression – After sustained clinical improvement is observed, gradually taper steroids (e.g., by 5 to 10 mg/week over 4 to 6 weeks) per institutional standards – Patients can be switched to an equivalent/appropriate dose of oral corticosteroids (e.g., prednisone) during the steroid taper

BAL = bronchoalveolar lavage; CMV = cytomegalovirus; COVID-19 = coronavirus 2019; CTCAE = Common Terminology Criteria for Adverse Events; DNA = deoxyribonucleic acid; HRCT = high-resolution computed tomography; ILD = interstitial lung disease; IV = intravenous; KL-6 = Krebs von den Lungen-6; PFT = pulmonary function test; PJP = *Pneumocystis jiroveci* fungus; RT-PCR = real-time polymerase chain reaction; SP-D = serum surfactant protein D; SpO2 = oxygen saturation.

Table 7 Dose Modification/Toxicity Management Recommendations for Diarrhea/Colitis

Adverse Reaction CTCAE V5.0 Grade/Severity	Recommended Management	Recommended Dosing Modification	Recommended Follow-up

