
Grade 1 or 2 Diarrhea (Mild or moderate, up to 6 episodes per day from baseline, and responsive to antidiarrheal treatment) OR Grade 1 Colitis (Asymptomatic)
	
 Monitor closely for any worsening of symptoms. Educate patient to report any worsening immediately Prompt evaluation for etiologies, including infection (with consideration of travel history and COVID-19), dietary factors, and medications, followed by diagnostic testing with stool culture, Clostridium difficile testing, CMV, parasite RT-PCR (if available), and COVID-19 testing (as appropriate) Consider supportive treatment (use of antidiarrheal and IV fluid resuscitation) and dietary optimization 	
Continue current dose and reassess in 48 hours
	
 Reassess within 48 hours of starting supportive treatment If responsive to antidiarrheal treatment: 
 No change in study drug dose Monitor as clinically indicated until complete resolution If not responsive to antidiarrheal treatment or worsening 
 Withhold study drug Manage as per next higher CTCAE grade

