
Grade 3 Diarrhea (Severe diarrhea, >6 episodes per day from baseline) OR Grade 2 or 3 Colitis (Abdominal pain, mucus or blood in stool, and peritoneal signs)
	
 Monitor symptoms every 1 to 2 days Evaluate differential diagnosis and causality (as described above) Consider GI consult/endoscopy for atypical or refractory cases Initiate supportive treatment (use of antidiarrheal and IV fluid resuscitation) and dietary optimization Administer prophylactic antimicrobial or appropriate treatment as per standard guidelines If determined as non-infectious (i.e., immune mediated), promptly start (including gradual tapering) enteric acting steroids (e.g., budesonide) or systemic steroids such as methylprednisolone IV 1 to 2 mg/kg/day or equivalent 	
Withhold study drug
	
 Continue close follow-up Reassess within 48 hours of starting supportive treatment 
 If resolves to Grade 1 or baseline with antidiarrheal treatment, restart study drug at the same dose level If considered infectious etiology (clearly not immune related): 
 If resolves to Grade 1 or baseline in <28 days, resume study drug at the same or a reduced dose at the clinical judgment/discretion of the investigator If considered non-infectious etiology with need for systemic steroid treatment, then permanently discontinue study drug 
 After sustained clinical improvement is observed, gradually taper steroids (e.g., by 5 to 10 mg/week over 4 to 6 weeks) per institutional standards

Adverse Reaction CTCAE V5.0 Grade/Severity	Recommended Management	Recommended Dosing Modification	Recommended Follow-up
			
 ○ Patients can be switched to an equivalent/appropriate dose of oral corticosteroids (e.g., prednisone) during the steroid taper ● If etiology unclear and resolves without a need for systemic steroid treatment, then study drug treatment may be restarted at a reduced dose based on investigator’s clinical judgment ● Monitor closely on restarting treatment; if symptoms recur at Grade 3 or higher, permanently discontinue the study drug

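### Tables 6 and 7 (Protocol Section 6.8) resume HMPL-689 after a resolved infection without excepting PJP or CMV; Table 9 stops drug permanently for these, and no visible text says that Table 9 governs

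*Protocol*

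**What the plan says.** All of the following is in Protocol Section 6.8.

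- **Table 6, Grade 2 pulmonary events.** The work-up includes "Infectious panel (consider bacterial, viral, and opportunistic infections, including PJP and CMV-use of cultures". The infectious branch opens "If considered infectious etiology (clearly not immune related". It then gives two resume rules: "If resolved in ≤7 days, resume study drug" and "If resolved in >7 to 28 days, resume study drug at the same or a reduced dose at the discretion of the investigator".
- **Table 6, Grade 3 or 4 pulmonary events.** The row carries the same work-up forward by reference and starts with "Hospitalize for further management". Its infectious branch reads "If resolved to baseline within 28 days, resume study drug at a reduced dose".
- **Table 7, Grade 3 diarrhea or Grade 2 or 3 colitis.** The work-up, set out in the row above and carried forward by reference, includes "CMV, parasite RT-PCR (if available), and COVID-19 testing (as appropriate". The infectious branch reads "If resolves to Grade 1 or baseline in <28 days, resume study drug at the same or a reduced dose", at the investigator's judgment.
- **Table 9, infection.** The Pneumocystis row calls for permanent discontinuation once PJP is diagnosed. The CMV row calls for it on CMV end-organ damage and lists colitis and pneumonitis among its examples.

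The introduction to Section 6.8 describes the tables as general recommendations, to be weighed with local standard of care and clinical judgment, and assigns infection to Table 9. Table 9 refers outward twice: its Grade 1 or 2 row to the pulmonary and gastrointestinal guidance, and its PJP row to Table 6 for management. Tables 6 and 7 do not refer to Table 9.

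**The concern.** A site treating pneumonia will naturally open the pulmonary table, and a site treating colitis the diarrhea and colitis table. Each prompts a search for the organisms at issue, then gives a resume rule for infectious events that does not set those organisms apart. A reader who stops there would restart drug in a patient for whom Table 9 recommends a permanent stop.

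What is at stake is re-exposure to a PI3Kδ inhibitor after an opportunistic infection. No endpoint or SAP analysis turns on it. The tables remain in use: under Amendment 5, enrolled patients who are benefiting may stay on drug, and supply to sites with active patients continues.

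**Working it through.** No arithmetic bears on the substance, and the plan gives no figure to reproduce. The check sets the tables side by side on three constructed cases.

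| Case (illustrative) | Pulmonary or diarrhea table | Table 9 |
|---|---|---|
| Grade 2 CMV pneumonitis, judged clearly infectious, resolved by day 7 | Table 6: resume | Stop permanently |
| Grade 3 PJP pneumonia, resolved to baseline by day 20 | Table 6: resume at a reduced dose | Stop permanently |
| Grade 3 CMV colitis, resolved to Grade 1 by day 20 | Table 7: resume at the same or a reduced dose | Stop permanently |

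**Extent in the text.** The affected follow-up cells are Table 6 Grade 2, Table 6 Grade 3 or 4, and Table 7 Grade 3 diarrhea or Grade 2 or 3 colitis: 1 + 1 + 1 = 3. Table 6 Grade 1 has no infectious branch. Table 7 Grade 4 already stops drug permanently. The PJP conflict arises only in Table 6. If the redacted Section 5.2.5 contains a PJP stop rule, the CMV conflict still touches all three cells. This counts places in the text and does not measure risk.

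**Is precedence stated elsewhere?**

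1. The Section 6.8 introduction lists which table covers which toxicity but does not rank them.
2. Section 5.4 refers to Section 6.8. Section 5.4.2 has its own rule to discontinue after more than 14 consecutive days of interruption, but it excepts events with additional guidance in Section 6.8, so it is not a dependable backstop.
3. The mandatory discontinuation list in Section 5.8.4 names neither organism.
4. Table 10 does refer to the infection guidance, next to its resume rule for Grade 4 neutropenia. That shows the kind of pointer missing from Tables 6 and 7. It does not decide which rule applies.

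**Which safeguards reach which case?**

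- *Grade 3 or 4 pulmonary events:* the row specifies hospitalization and a pulmonary or infectious disease consult. An event reported as serious reaches the sponsor within 24 hours (Section 6.4).
- *Grade 2 pulmonary events:* the consult is requested only when the cause is unclear, so an identified organism may not trigger it. However, Section 6.2.3 makes non-serious interstitial lung disease or pneumonitis an adverse event of special interest, reportable within 24 hours, and points to Table 6. Grade 2 CMV pneumonitis is plausibly covered; PJP is less clearly so under that wording.
- *Colitis:* Table 7 advises only considering a gastrointestinal consult or endoscopy, for atypical or refractory cases. Non-serious CMV colitis is not among the events named in Section 6.2.3, so this case is least covered.

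Reporting to the sponsor is not an approval step before resuming in any of these cases.

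**The case against.** The strongest reply is that only one reading gives Table 9 its full effect. If Tables 6 and 7 governed once an event resolved in time, the permanent stops in Table 9 would be largely empty for the very events they name. The PJP row cites Table 6 for management and still sets its own stop, so Table 6 was in view when the stop was written. Table 9's own Grade 3 or higher infection row also resumes drug after resolution to baseline within 28 days, with no PJP or CMV exception, and the organism rows below it are plainly meant to override it. The introduction sends infection to Table 9, and a site that has identified PJP or CMV has diagnosed an infection.

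Most of this stands. It shows which rule is intended, and it defeats a stronger reading that a reader might draw: that the protocol directs rechallenge after PJP or CMV disease. It does not show that a site working from Table 6 or 7 will be led to Table 9. Within Table 9 the general and specific rows are in one table; across tables there is no pointer toward the specific row.

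The advisory status of Section 6.8, its invitation to discuss questions promptly with the sponsor, and the halt to enrollment also count toward a lower rating.

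**Conclusion.** The inconsistency is real in three cells and is a minor safety clarification. Read alone, Tables 6 and 7 give a resume instruction where Table 9 gives a permanent stop. Table 9's organism rows are the natural governing rule, but that must be inferred.

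The residual risk is reduced by the advisory status of the tables, the routing of infection to Table 9, infectious disease consults, and 24-hour reporting of serious events and of non-serious pneumonitis. It is least reduced for non-serious CMV colitis.

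The conclusion rests on visible text. Section 5.2.5, on PJP prophylaxis, is redacted and could settle the PJP part; on the visible text, the CMV part would remain. The documents give no PJP or CMV incidence for this drug and no visible number of patients still on treatment, so no frequency can be stated. A reader might also infer that patients have already been wrongly restarted; nothing in the documents supports that.

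**What to change.** Add one sentence to Section 6.8 stating that the PJP and CMV rows of Table 9 override the resume branches of Tables 6 and 7.

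An equivalent alternative is to edit the cells. The Table 6 Grade 2 and Grade 3 or 4 infectious branches would except PJP and CMV, with permanent discontinuation per Table 9. The Table 7 infectious branch would except CMV colitis in the same way. The single sentence is the smaller change.

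In either case, notify sites that still have patients on drug.

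The cost is a small protocol clarification, the IRB/IEC notification that Section 8.1 requires for protocol changes, and one site letter. It needs no new visit, test or data.
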